11.2 Adherence to the Protocol

The investigator will conduct the study in strict accordance with the protocol (refer to ICH E6, Section 4.5).

11.3 Monitoring Procedures

The sponsor's or CRO's CRA will maintain contact with the investigator and designated staff by telephone, letter, or email between study visits. Monitoring visits to each site, and potential remote source document verification, will be conducted by the assigned CRA as described in the monitoring plan. The investigator (or if regionally required, the head of the medical institution) will allow the CRA to inspect the clinical, laboratory, and pharmacy facilities to assure compliance with GCP and local regulatory requirements. The eCRFs and subject's corresponding original medical records (source documents) are to be fully available for review by the sponsor's representatives at regular intervals. These reviews verify adherence to study protocol and data accuracy in accordance with local regulations. All records at the site are subject to inspection by the local auditing agency and to IRB/IEC review.

In accordance with ICH E6, Section 1.52, source documents include, but are not limited to, the following:

- Clinic, office, or hospital charts
- Copies or transcribed health care provider notes that have been certified for accuracy after production
- Recorded data from automated instruments such as IxRS, x-rays, and other imaging reports (eg, sonograms, computed tomography scans, MRIs, radioactive images, ECGs, rhythm strips, electroencephalography, polysomnographs, pulmonary function tests) regardless of how these images are stored, including microfiche and photographic negatives
- Pain, quality of life, or medical history questionnaires completed by subjects
- Records of telephone contacts
- Diaries or evaluation checklists
- Drug distribution and accountability logs maintained in pharmacies or by research personnel
- Laboratory results and other laboratory test outputs (eg, urine pregnancy test result documentation and urine dip-sticks)
- Correspondence regarding a study subject's treatment between physicians or memoranda sent to the IRBs/IECs
- CRF components (eg, questionnaires) that are completed directly by subjects and serve as their own source

11.4 Recording of Data

An eCRF is required and must be completed for each subject by qualified and authorized personnel. All data on the eCRF must reflect the corresponding source document, except when a section of the eCRF itself is used as the source document. Any correction to entries made on the eCRF must be documented in a valid audit trail where the correction is dated, the individual making the correction is identified, the reason for the change is stated, and the original data are not obscured. Only data required by the protocol for the purposes of the study should be collected.

The investigator must sign each eCRF. The investigator will report the eCRFs to the sponsor and retain a copy of the eCRFs.

11.5 Identification of Source Data

All data to be recorded on the eCRF must reflect the corresponding source documents.

11.6 Retention of Records

The circumstances of completion or termination of the study notwithstanding, the investigator (or if regionally required, the head of the medical institution or the designated representative) is responsible for retaining all study documents, including but not limited to the protocol, copies of eCRFs, the Investigator's Brochure, and regulatory agency registration documents (eg, Form FDA 1572, ICFs, and IRB/IEC correspondence). The site should plan to retain study documents, as directed by the sponsor, for at least 2 years after the last approval of a marketing application in an ICH region and until there are no pending or contemplated marketing applications in an ICH region or at least 3 years have elapsed since the formal discontinuation of clinical development of the investigational product.

It is requested that at the completion of the required retention period, or should the investigator retire or relocate, the investigator contact the sponsor, allowing the sponsor the option of permanently retaining the study records.

11.7 Auditing Procedures and Inspection

In addition to routine monitoring procedures, the sponsor's Clinical Quality Assurance department conducts audits of clinical research activities in accordance with the sponsor's standard operating procedures to evaluate compliance with the principles of ICH GCP and all applicable local regulations. If a government regulatory authority requests an inspection during the study or after its completion, the investigator must inform the sponsor immediately.

11.8 Handling of Study Drug

All study drug will be supplied to the principal investigator (or a designated pharmacist) by the sponsor. Drug supplies must be kept in an appropriate secure area (eg, locked cabinet) and stored according to the conditions specified on the drug labels. The investigator (or a designated pharmacist) must maintain an accurate record of the shipment and dispensing of the study drug in a drug accountability ledger, a copy of which must be given to the sponsor at the end of the study. An accurate record of the date and amount of study drug dispensed to each subject must be available for inspection at any time. The CRA will visit the site and review these documents along with all other study conduct documents at appropriate intervals once study drug has been received by the site.

All drug supplies are to be used only for this study and not for any other purpose. The investigator (or site personnel) must not destroy any drug labels or any partly used or unused drug supply before approval to do so by the sponsor. At the conclusion of the study and as appropriate during the study, the investigator (or a designated pharmacist) will return all used and unused drug containers, drug labels, and a copy of the completed drug disposition form to the sponsor's CRA (or designated contractor).

11.9 Publication of Results

All manuscripts, abstracts, or other modes of presentation arising from the results of the study must be reviewed and approved in writing by the sponsor in advance of submission pursuant to the terms and conditions set forth in the executed CTA between the sponsor/CRO and the institution/investigator. The review is aimed at protecting the sponsor's proprietary information existing either at the date of the commencement of the study or generated during the study. The detailed obligations regarding the publication of any data, material results, or other information generated or created in relation to the study shall be set out in the agreement between each investigator and the sponsor or CRO, as appropriate.

11.10 Disclosure and Confidentiality

The contents of this protocol and any amendments and results obtained during the study should be kept confidential by the investigator, the investigator's staff, and the IRB/IEC and will not be disclosed in whole or in part to others, or used for any purpose other than reviewing or performing the study, without the written consent of the sponsor. No data collected as part of this study will be used in any written work, including publications, without the written consent of the sponsor. These obligations of confidentiality and non-use shall in no way diminish such obligations as set forth in either the Confidentiality Agreement or CTA executed between the sponsor/CRO and the institution/investigator. All persons assisting in the performance of this study must be bound by the obligations of confidentiality and non-use set forth in either the Confidentiality Agreement or CTA executed between the institution/investigator and the sponsor/CRO.

11.11 Discontinuation of Study

The sponsor reserves the right to discontinue the study for medical reasons or any other reason at any time. If a study is prematurely terminated or suspended, the sponsor will promptly inform the investigators/institutions and regulatory authorities of the termination or suspension and the reason(s) for the termination or suspension. The IRB/IEC will also be informed promptly and provided the reason(s) for the termination or suspension by the sponsor or by the investigator/institution, as specified by the applicable regulatory requirement(s).

The investigator reserves the right to discontinue the study should his/her judgment so dictate. If the investigator terminates or suspends a study without prior agreement of the sponsor, the investigator should inform the institution where applicable, and the investigator/institution should promptly inform the sponsor and the IRB/IEC and provide the sponsor and the IRB/IEC with a detailed written explanation of the termination or suspension. Study records must be retained as noted above.

11.12 Subject Insurance and Indemnity

The sponsor will provide insurance for any subjects participating in the study in accordance with all applicable laws and regulations.

12 APPENDICES

Appendix 1 Sponsor's Grading for Laboratory Values

(revised per Amendment 01)

| | Grade 1 | Grade 2 | Grade 3 | Grade 4 |
|--|---|---|---|---|
| BLOOD/BONE MARROW | | | | |
| Hemoglobin (conversion from g/dL×0.6206) | Female (ULN=15.9 g/dL) <11.1 – 10.0 g/dL <111 – 100 g/L <6.9 – 6.2 mmol/L Male (ULN=17.7 g/dL) <12.6 – 10.0 g/dL <126 – 100 g/L <7.8 – 6.2 mmol/L | <10.0 – 8.0 g/dL <100 – 80 g/L <6.2 – 4.9 mmol/L | <8.0 g/dL <80 g/L <4.9 mmol/L; transfusion indicated | life-threatening consequences; urgent intervention indicated |
| Leukocytes (total white blood cell) | <3.40 – 3.0×10 ⁹ /L <3.40 10 ³ /uL – 3000/mm ³ (ULN=10.80 10 ³ /μL) | <3.0 – 2.0×10 ⁹ /L <3000 – 2000/mm ³ | <2.0 – 1.0×10 ⁹ /L <2000 – 1000/mm ³ | <1.0×10 ⁹ /L <1000/mm ³ |
| Lymphocytes | not applicable | <700 – 500/mm ³ <0.7 – 0.5×10 ⁹ /L | <500 – 200/mm ³ <0.5 – 0.2×10 ⁹ /L | <200/mm ³ <0.2×10 ⁹ /L |
| Neutrophils | not applicable | <1.4 – 1.0×10 ⁹ /L <1400 – 1000/mm ³ | <1.0 – 0.5×10 ⁹ /L <1000 – 500/mm ³ | <0.5×10 ⁹ /L <500/mm ³ |
| Platelets | <155 – 75.0×10 ⁹ /L <155 10 ³ /uL – 75,000/mm ³ (ULN=379 10 ³ /μL) | <75.0 – 50.0×10 ⁹ /L <75,000 – 50,000/mm ³ | <50.0 – 25.0×10 ⁹ /L <50,000 – 25,000/mm ³ | <25.0×10 ⁹ /L <25,000/mm ³ |
| METABOLIC/LABORATORY | | | | |
| Albumin, serum- low (hypoalbuminemia) | 2 - 59 years (ULN=5.5 g/dL) <3.5 – 3 g/dL <35 – 30 g/L 59 -69 years (LLN-ULN) <3.6 g/dL – 3 g/dL 69 -79 years (LLN-ULN) <3.5 g/dL – 3g/dL 79 -89 years (LLN-ULN) <3.5g/dL – 3g/dL | <3 – 2 g/dL <30 – 20 g/L | <2 g/dL <20 g/L | life-threatening consequences; urgent intervention indicated |
| Alkaline phosphatase | Female: 18 -19 years >101 – 3.0×101 19 -61 years ULN=107 61 -71 years ULN=112 71 -150 years ULN=108 Male 18 -19 years >127 – 3.0×127 19 -61 years ULN=102 61 -71 years ULN=103 71 -150 years ULN=105 | >3.0 – 5.0×ULN See previous column for ULN values | >5.0 – 20.0×ULN See previous column for ULN values | >20.0×ULN See previous column for ULN values |
| Alanine aminotransferase | Female: >32 – 3.0×32 | Female: >3.0 – 5.0×32 | Female: >5.0 – 20.0×32 | Female: >20.0×32 |

| | Grade 1 | Grade 2 | Grade 3 | Grade 4 |
|---|--|--|---|---|
| | Male: >44 – 3.0 x 44 | Male >3.0 – 5.0x44 | Male: >5.0 – 20.0x44 | Male: >20.0x44 |
| Aspartate aminotransferase | >40 – 3.0x40 | >3.0 – 5.0x40 | >5.0 – 20.0x40 | >20.0x40 |
| Bilirubin (hyperbilirubinemia) | >1.2 – 1.5x1.2 | >1.5 – 3.0x1.2 | >3.0 – 10.0x1.2 | >10.0x1.2 |
| Calcium, serum-low (hypocalcemia) (conversion to mmolx0.25) | <8.5 – 8.0 mg/dL <2.13 – 2.0 mmol/L | <8.0 – 7.0 mg/dL <2.0 – 1.75 mmol/L | <7.0 – 6.0 mg/dL <1.75 – 1.5 mmol/L | <6.0 mg/dL <1.5 mmol/L |
| Calcium, serum-high (hypercalcemia) | >10.6 – 11.5 mg/dL >2.65 – 2.9 mmol/L | >11.5 – 12.5 mg/dL >2.9 – 3.1 mmol/L | >12.5 – 13.5 mg/dL >3.1 – 3.4 mmol/L | >13.5 mg/dL >3.4 mmol/L |
| Cholesterol, serum-high (hypercholesterolemia) (conversion to mmol/L x0.02586) | 0 -19 years >169 – 300 mg/dL >4.37 – 7.75 mmol/L 19 -150 years >199 – 300 mg/dL >5.15 – 7.75 mmol/L | >300 – 400 mg/dL >7.75 – 10.34 mmol/L | >400 – 500 mg/dL >10.34 – 12.92 mmol/L | >500 mg/dL >12.92 mmol/L |
| Creatinine | Female >1.00 mg/dL – 1.5x1.00 Male >1.27 mg/dL – 1.5x1.27 | Female >1.5 – 3.0x1.00 Male >1.5 mg/dL – 3.0x1.27 | Female >3.0 – 6.0x1.00 Male >3.0 mg/dL – 6.0 x1.27 | Female >6.0x1.00 Male >6.0x1.27 |
| Gamma glutamyl transpeptidase | Female >60 IU/L – 3.0x60 Male >65 IU/L – 3.0x65 | Female >3.0 – 5.0x60 Male >3.0 – 5.0x65 | Female >5.0 – 20.0x60 Male >5.0 – 20.0x65 | Female >20.0x60 Male >20.0x65 |
| Glucose, serum-high (hyperglycemia) (conversion to mmol/L x0.0555) | Fasting glucose value >99 – 160 mg/dL >5.5 – 8.9 mmol/L | Fasting glucose value >160 – 250 mg/dL >8.9 – 13.9 mmol/L | >250 – 500 mg/dL; >13.9 – 27.8 mmol/L; hospitalization indicated | >500 mg/dL; >27.8 mmol/L; life-threatening consequences |
| Glucose, serum-low (hypoglycemia) | <65 – 55 mg/dL <3.6 – 3.0 mmol/L | <55 – 40 mg/dL <3.0 – 2.2 mmol/L | <40 – 30 mg/dL <2.2 – 1.7 mmol/L | <30 mg/dL <1.7 mmol/L life-threatening consequences; seizures |
| Phosphate, serum-low (hypophosphatemia) (conversion to mmol/L x0.323) | not applicable | <2.5 – 2.0 mg/dL <0.8 – 0.6 mmol/L | <2.0 – 1.0 mg/dL <0.6 – 0.3 mmol/L | <1.0 mg/dL <0.3 mmol/L life-threatening consequences |
| Potassium, serum-high (hyperkalemia) | not applicable | >5.5 – 6.0 mmol/L | >6.0 – 7.0 mmol/L hospitalization indicated | >7.0 mmol/L life-threatening consequences |
| Potassium, serum-low (hypokalemia) | <3.5 mEq/L – 3.0 mmol/L | <LLN – 3.0 mmol/L; symptomatic; intervention indicated | <3.0 – 2.5 mmol/L hospitalization indicated | <2.5 mmol/L life-threatening consequences |
| Sodium, serum-high (hypernatremia) | >144 mEq/L – 150 mmol/L | >150 – 155 mmol/L | >155 – 160 mmol/L hospitalization indicated | >160 mmol/L life-threatening consequences |
| Sodium, serum-low (hyponatremia) | <134 mEq/L – 130 mmol/L | Not applicable | <130 – 120 mmol/L | <120 mmol/L life-threatening consequences |
| Triglyceride, serum-high (hypertriglyceridemia) | 150 – 300 mg/dL 1.71 – 3.42 mmol/L | >300 – 500 mg/dL >3.42 – 5.7 mmol/L | >500 – 1000 mg/dL >5.7 – 11.4 mmol/L | >1000 mg/dL >11.4 mmol/L life-threatening consequences |

| | Grade 1 | Grade 2 | Grade 3 | Grade 4 |
|---------------------------------------|--|----------------|--|--|
| Uric acid, serum-high (hyperuricemia) | Female >7.1 – 10 mg/dL Male >8.6 – 10 mg/dL Both ≤0.59 mmol/L without physiologic consequences | Not applicable | Female >7.1 – 10 mg/dL Male >8.6 – 10 mg/dL Both ≤0.59 mmol/L without physiologic consequences | >10 mg/dL >0.59 mmol/L life-threatening consequences |

LLN = lower limit of normal, ULN = upper limit of normal.

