9.7.1.1 Study Endpoints

9.7.1.1.1 PRIMARY ENDPOINT

- Safety and tolerability, which include incidence of TEAEs and SAEs, laboratory parameters, vital signs, and ECG parameters (revised per Amendment 05)

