9.7.1.8.3 LABORATORY VALUES

Laboratory results will be summarized using International System of Units, as appropriate. For all quantitative parameters listed in [Section 9.5.1.5.3](#), the actual value and the change from baseline to each postbaseline visit and to the end of treatment (defined as the last on-treatment value) will be summarized by visit and treatment group using descriptive statistics. Qualitative parameters listed in [Section 9.5.1.5.3](#) will be summarized using frequencies (number and percentage of subjects), and changes from baseline to each postbaseline visit and to end of treatment will be reported using shift tables. Percentages will be based on the number of subjects with both nonmissing baseline and relevant postbaseline results.

Laboratory test results will be assigned a low/normal/high (LNH) classification according to whether the value was below (L), within (N), or above (H) the laboratory parameter's reference range. Within-treatment comparisons for each laboratory parameter will be based on 3-by-3 tables (shift tables) that compare the baseline LNH classification to the LNH classification at each postbaseline visit and at the end of treatment. Similar shift tables will also compare the baseline LNH classification to the LNH classification for the highest and lowest value during the treatment period.

[Appendix 1](#) (Sponsor's Grading for Laboratory Values) presents the criteria that will be used to identify subjects with treatment-emergent markedly abnormal laboratory values (TEMAVs). Except for phosphate, a TEMAV is defined as a postbaseline value with an increase from baseline to a Grade of 2 or higher. For phosphate, a TEMAV was defined as a postbaseline value with an increase from baseline to a Grade of 3 or higher. When displaying the incidence of TEMAVs, each subject may be counted once in the laboratory parameter high and in the laboratory parameter low categories, as applicable.

Lymphocyte subsets measured (including but not limited to CD4 [T helper cells], CD8 [cytotoxic T cells], CD19 [B cells], CD16/CD56 [natural killer cells] and CD14 [macrophages] and regulatory T cells) will be summarized in the same manner as other laboratory parameters. Mean lymphocyte subsets and the mean change from baseline in lymphocyte subsets will also be displayed graphically over time by dose.

Serum IgG, IgM, and IgA will be measured and summarized in the same manner as other laboratory parameters.

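### Two rows of Appendix 1 contradict themselves: uric acid Grades 1 and 3 are identical and adjacent male creatinine grades overlap, leaving TEMAV status or severity unsettled for some values

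*Protocol*

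**What the plan says.** Section 9.7.1.8.3 (Laboratory Values) states that Appendix 1 "presents the criteria that will be used to identify subjects with treatment-emergent markedly abnormal laboratory values (TEMAVs"). The rule follows: "Except for phosphate, a TEMAV is defined as a postbaseline value with an increase from baseline to a Grade of 2 or higher". For phosphate the threshold is Grade 3.

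In the uric acid row of Appendix 1, Grade 1 and the Grade 2 entry read "Female >7.1 – 10 mg/dL Male >8.6 – 10 mg/dL Both ≤0.59 mmol/L without physiologic consequences | Not applicable". Grade 2, Grade 3 and the start of Grade 4 read "Not applicable | Female >7.1 – 10 mg/dL Male >8.6 – 10 mg/dL Both ≤0.59 mmol/L without physiologic consequences | >10 mg/dL". Where the first three cells meet, the row runs "without physiologic consequences | Not applicable | Female >7.1".

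In the creatinine row, male Grade 1 is "Male >1.27 mg/dL – 1.5x1.27". The Grade 2 cell opens "Female >1.5 – 3.0x1.00 Male >1.5 mg/dL" and its male upper bound is 3.0 × 1.27. Male Grade 3 starts above 3.0 mg/dL and ends at 6.0 × 1.27. Male Grade 4 is anything above 6.0 × 1.27.

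Section 9.7.1.1.1 gives the primary endpoint as "Safety and tolerability, which include incidence of TEAEs and SAEs, laboratory parameters, vital signs, and ECG parameters".

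**The concern.** A grading table used to derive a yes/no flag has to give each value one grade. These two rows do not, and in both the ambiguity crosses the line between Grade 1 (no TEMAV) and a TEMAV grade. Two programmers following the protocol faithfully could report different TEMAV counts from the same data, and nothing in the text would say which is right.

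The arms are small. Section 9.7.2 plans about 15 subjects per dose group, so one subject whose flag changes moves an arm's incidence by 1/15, or about 6.7 percentage points. That shows the scale only; it is not a forecast of how many subjects are affected.

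**Working it through.** There is no sample size or power figure to reproduce. The check codes each grade as printed (above the lower bound, up to and including the upper bound) and looks for values that receive more than one grade.

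**Uric acid (mg/dL)**

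| Grade | Women | Men | Qualifier |
|---|---|---|---|
| 1 | >7.1 to 10 | >8.6 to 10 | no physiologic consequences |
| 2 | none | none | none |
| 3 | >7.1 to 10 | >8.6 to 10 | no physiologic consequences |
| 4 | >10 | >10 | life-threatening consequences |

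A woman at 7.2, 8.0, 9.0 or 10 is Grade 1 and Grade 3. A man at 9.0 or 10 is Grade 1 and Grade 3. Only values above 10 have a single grade. The hypokalemia row also gives Grades 1 and 2 nearly the same range, but its Grade 2 adds symptoms and a need for intervention. The uric acid row has no such separator, because the qualifier is repeated along with the numbers.

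**Male creatinine (mg/dL)**, with reference limit 1.27

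- 1.5 × 1.27 = 1.905
- 3.0 × 1.27 = 3.81
- 6.0 × 1.27 = 7.62

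| Grade | As printed | Lower bounds read as multiples |
|---|---|---|
| 1 | >1.27 to 1.905 | >1.27 to 1.905 |
| 2 | >1.5 to 3.81 | >1.905 to 3.81 |
| 3 | >3.0 to 7.62 | >3.81 to 7.62 |
| 4 | >7.62 | >7.62 |

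As printed there are two overlaps:

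- Grades 1 and 2, above 1.5 up to 1.905. This is (1.905 − 1.5) / (1.905 − 1.27) = 0.405 / 0.635 = 64% of the Grade 1 interval. It begins at 1.5 / 1.27 = 1.18 times the reference limit.
- Grades 2 and 3, above 3.0 up to 3.81.

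A man at 1.6, 1.8 or 1.9 is Grade 1 and Grade 2 as printed, but Grade 1 only when the lower bounds are multiples. At 3.2 or 3.8 he is Grade 2 and Grade 3 as printed, but Grade 2 only as multiples. Read as multiples, the four grades meet without gap or overlap.

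Women are unaffected. Their reference limit is 1.00, so 1.5 mg/dL and 1.5 × 1.00 are the same number.

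**Consequence for the TEMAV flag.** The first overlap joins a non-TEMAV grade to a TEMAV grade, so it can change counts. It can do so in either direction. A man rising from 1.2 to 1.6 is added if the higher grade is used. A man already at 1.6 at baseline who reaches 2.5 would start at Grade 2 under that choice, show no increase in grade, and be lost. In the second overlap both grades are TEMAV grades, so a man who starts below Grade 2 is counted either way and only his severity changes.

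**The case against.** The strongest reply is that the creatinine row is a stray unit with a recoverable meaning. Every other male bound above the reference limit is a multiple of 1.27. The female creatinine row and the ALT, AST, bilirubin and GGT rows give the corresponding bounds as multiples without a unit. That is persuasive about intent, and creatinine is the weaker of the two defects. The printed row still contradicts itself. If the central laboratory really does grade from 1.5 mg/dL, the Grade 1 upper bound of 1.905 is then the wrong entry. The revision history says Amendment 01 aligned the creatinine grading with the central laboratory's values. That source is not in the protocol, so the correction should be checked against it. Uric acid is not among the analytes that amendment lists as revised, and its intended Grade 3 cannot be recovered from the document.

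A second reply is that little depends on this. TEMAV incidence is one descriptive display. Section 9.7.1.8.3 also reports actual values, change from baseline, and shift tables built on reference ranges, none of which uses the Appendix 1 grades. The Core Study discontinuation criteria in Section 9.3.3 use neither analyte. All of this stands and limits the weight of the point.

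Three stronger readings are tempting but unsupported.

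- A reader might infer that TEMAV counts in general, or the primary endpoint, are compromised. The endpoint names laboratory parameters broadly, and the contradiction is shown for two rows only.
- A reader might infer that every uric acid value in the band becomes a Grade 3 TEMAV. Two identical cells do not dictate the higher grade; a program testing Grade 1 first would flag nothing up to 10 mg/dL. A subject already in the band at baseline who stays there also shows no increase in grade.
- A reader might infer that every overlap crosses the TEMAV threshold. The one above 3.0 mg/dL does not.

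**Conclusion.** The point holds for two rows of Appendix 1. For uric acid, TEMAV status is undefined for all values above the upper limit up to 10 mg/dL in both sexes. For creatinine in men, values above 1.5 up to 1.905 mg/dL are both Grade 1 and Grade 2, which can change TEMAV counts; values above 3.0 up to 3.81 mg/dL are both Grade 2 and Grade 3, which changes severity.

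The severity-only conclusion assumes the man is below Grade 2 at baseline. A man already in Grade 2 who moves into the second overlap could be counted or not, depending on the grade chosen. Exclusion criterion 24 (clinically significant laboratory deviation at Screening or Baseline) makes such an entry value unlikely.

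The effect is limited to TEMAV incidence and severity for these two analytes. How many subjects fall in the bands cannot be derived from the protocol. This should be corrected because the protocol itself fixes these thresholds, but it does not bear on the design or on the other laboratory summaries.

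**What to change.** Before TEMAVs are tabulated, reconcile both rows with the central laboratory's grading source.

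- **Uric acid:** make Grades 1 and 3 distinguishable. If they differ only by a clinical consequence that is not in the laboratory data, leave that Grade 3 out of the automatic TEMAV derivation and say so.
- **Male creatinine:** write Grade 2 as >1.5–3.0 × 1.27 and Grade 3 as >3.0–6.0 × 1.27, in line with the female row and the other rows based on multiples of the upper limit. If the laboratory's grading shows that plain 1.5 and 3.0 mg/dL are intended, change the Grade 1 and Grade 2 upper bounds to match instead.

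The cost is two corrected table rows and the matching lines of the TEMAV derivation specification, settled before database lock. No additional data are needed.
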